## 7.6 Safety

Analyses in this section will be tabulated for all treated subjects by treatment group as treated, unless otherwise specified.

In addition, selected safety analyses (including any adverse events (AE), drug-related AE, serious AEs, drug-related SAE, AEs leading to discontinuation, drug-related AE leading to discontinuation, death summary) will be summarized by treatment group in all treated PD-L1 expressing subjects and all treated PD-L1 negative subjects. In all treated PD-L1 expressing subjects, the frequency of immune mediated adverse events and other events of special interest (within 100 days), select AEs and drug-related select AEs (within 30 days) will be summarized by treatment group.

#### 7.6.1 Deaths

Deaths will be summarized by treatment group:

- All deaths, reasons for death.
- Deaths within 30 days of last dose received, reasons for death.
- Deaths within 100 days of last dose received, reasons for death.

A by-subject listing of deaths will be provided for the all enrolled subjects population.

#### 7.6.2 Serious Adverse Events

Serious adverse events will be summarized by treatment group:

- Overall summary of SAEs by worst CTC grade (any grade, grade 3-4, grade 5) presented by SOC/PT.
- Overall summary of drug-related SAEs by worst CTC grade (any grade, grade 3-4, grade 5) presented by SOC/PT.

All analyses will be conducted using the 30-day safety window.

A by-subject SAE listing will be provided for the "enrolled subjects" population.

## 7.6.3 Adverse Events Leading to Discontinuation of Study Therapy

AEs leading to discontinuation will be summarized by treatment group:

• Overall summary of AEs leading to discontinuation by worst CTC grade (any grade, grade 3-4, grade 5) presented by SOC/PT.

• Overall summary of drug-related AEs leading to discontinuation by worst CTC grade (any grade, grade 3-4, grade 5) presented by SOC/PT.

The analyses will be conducted using the 30-day safety window.

A by-subject AEs leading to discontinuation listing will be provided.

#### 7.6.4 Adverse Events Leading to Dose Modification

AEs leading to dose delay/reduction will be summarized by treatment group:

- Overall summary of AEs leading to dose delay/reduction by worst CTC grade (any grade, grade 3-4, grade 5) presented by SOC/PT.
- Overall summary of related AEs leading to dose delay/reduction by worst CTC grade (any grade, grade 3-4, grade 5) presented by SOC/PT.

The analysis will be conducted using the 30-day safety window.

A by-subject AEs leading to dose delay/reduction listing will be provided.

#### 7.6.5 Adverse Events

Adverse events will be summarized by treatment group.

The following analyses will be conducted using the 30 days safety window only:

- Overall summary of any AEs by worst CTC grade (1, 2, 3, 4, 5, not reported) presented by SOC/PT.
- Overall summary of any AEs presented by worst CTC grade (any grade, grade 3-4, grade 5) by SOC/PT. This table will be restricted to events with an incidence greater or equal to 5% in any treatment group.
- Overall summary of any non-serious AEs presented by SOC/PT. This table will be restricted to events with an incidence greater or equal to 5% in any treatment group.
- Overall summary of any AEs that required immune modulating medication by worst CTC grade (any grade, grade 3-4, grade 5) presented by SOC/PT.
- Overall summary of drug-related AEs by worst CTC grade (1, 2, 3, 4, 5, not reported) presented by SOC/PT.

The following analyses will be conducted using the 30 days safety window and repeated using the 100 days safety window:

• Overall summary of drug-related AEs by worst CTC grade (any grade, grade 3-4, grade 5) presented by SOC/PT.

A by-subject AE listing will be provided. A by-subject listing of any AE requiring immune modulating medications will also be provided.

#### 7.6.6 Select Adverse Events

Unless otherwise specified, analyses will be performed by select AE category. Analyses will also be repeated by subcategory of endocrine events.

#### 7.6.6.1 Incidence of Select AE

Select AEs will be summarized by treatment group for each category/subcategory.

The following analyses will be conducted using the 30-day safety window only:

- Overall summaries of any select AEs by worst CTC grade (any grade, grade 3-4, grade 5) presented by Category or Subcategory/PT.
- Overall summaries of any drug-related select AEs by worst CTC grade (any grade, grade 3-4, grade 5) presented by Category or Subcategory/PT.
- Overall summaries of any serious select AEs by worst CTC grade (any grade, grade 3-4, grade 5) presented by Category or Subcategory /PT.
- Overall summaries of drug-related serious select AEs by worst CTC grade (any grade, grade 3-4, grade 5) presented by Category or Subcategory /PT.
- Overall summaries of any select AEs leading to discontinuation by worst CTC grade (any grade, grade 3-4, grade 5) presented by Category or Subcategory /PT.
- Overall summaries of drug-related select AEs leading to discontinuation by worst CTC grade (any grade, grade 3-4, grade 5) presented by Category or Subcategory /PT.
- Summary of frequency of unique select AEs by Category.

A by-subject select AE listing will be provided.

#### 7.6.6.2 Time-to Onset of Select AE

Time-to onset of drug-related select AEs (any grade, grade 3-5) will be summarized for each category/subcategory by treatment group.

Time-to onset analyses are restricted to treated subjects who experienced at least one drug-related select AE in the category/subcategory. The analyses will be conducted using the 30-day safety window.

Additional details regarding the time-to onset definition are described in time-to onset definition subsection of APPENDIX 3.

#### 7.6.6.3 Time-to Resolution of Select AE

Time-to resolution of the following specific events will be summarized separately for each category/subcategory.

- Time-to resolution of drug-related select AE (any grade, grade 3-5) by treatment group
- Time-to resolution of drug-related select AE (any grade, grade 3-5) where immune modulating medication was initiated, by treatment group

Time-to resolution analyses are restricted to treated subjects who experienced the specific events. Time-to resolution where immune modulating medication was initiated analyses are restricted to treated subjects who experienced the specific events and who received immune modulating medication during the longest select AE.

The analyses will be conducted using the 30-day safety window.

The following summary statistics will be reported: percentage of subjects with resolution of the longest select AE, median time-to resolution along with 95% CI (derived from Kaplan-Meier estimation) and ranges.

See time-to resolution definition subsection of APPENDIX 3 for additional details.

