Premedications for use with fluorouracil/cisplatin: Antiemetic premedication will be administered according to local standards. Recommended antiemetic treatments are dexamethasone (dosing according to local standards; an equivalent dose of another corticosteroid may be substituted) and a 5-HT3 receptor antagonist (type per investigator discretion and local standards-of-care). Dexamethasone is allowed as premedication in arm B during the platinum-based chemotherapy. Additional use of antiemetic premedications may be employed at the discretion of the Investigator. Refer to the local product label for more detail. There are no premedications recommended for nivolumab treatment.

Doses of fluorouracil and/or cisplatin may be interrupted, delayed, reduced, or discontinued depending on how well the subject tolerates the treatment. See the following [sections](#) for more details: [4.5.2](#) (dose delays) and [4.5.3](#) (dose reductions), [4.5.4](#) (retreatment), and [4.5.5](#) (dose discontinuations).

If either fluorouracil or cisplatin is discontinued the other study treatments may be continued for the remainder of the cycles.

In subjects who required fluorouracil dose reduction due to toxicity during the fluorouracil/cisplatin combination cycles, the dose of fluorouracil may be re-escalated to 800 mg/m^2 after the discontinuation of cisplatin, at the investigator’s discretion and according to local standards, if the prior toxicity was felt to be related mainly to cisplatin.

All subjects who will be receiving cisplatin should have audiometric testing performed prior to initiation of therapy and prior to subsequent doses of cisplatin, or as per local standards of care.

Doses of nivolumab may be interrupted, delayed, or discontinued depending on how well the subject tolerates the treatment. There will be no dose escalations or reductions of nivolumab allowed. Subjects may be dosed with nivolumab no less than 12 days from the previous dose of nivolumab.

Subjects should be carefully monitored for infusion reactions during nivolumab administration. If an acute infusion reaction is noted, subjects should be managed according to [Section 4.5.8](#).

Treatment Group	Drug Name	Cycle 1 (Week 1)	Cycle 2 (Week 5)	Cycle 3 (Week 9)	Cycle 4 (Week 13)	Cycle 5 (Week 17)	Cycle 6 (Week 21) till EOT

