**Premedications:** Antiemetic premedication will be administered according to local standards. Recommended antiemetic treatments are dexamethasone (dosing according to local standards; an equivalent dose of another corticosteroid may be substituted) and a 5-HT3 receptor antagonist (type per investigator discretion and local standards-of-care). Dexamethasone is allowed as premedication in arm C during the platinum-based chemotherapy. Refer to the local product label for more detail. Additional use of antiemetic premedications may be employed at the discretion of the Investigator.

All subjects who will be receiving cisplatin should have audiometric testing performed prior to initiation of therapy and prior to subsequent doses of cisplatin, or as per local standards of care.

Treatment Group	Drug Name	Cycle 1 (Week 1)	Cycle 2 (Week 5)	Cycle 3 (Week 9)	Cycle 4 (Week 13)	Cycle 5 (Week 17)	Cycle 6 (Week 21) till EOT
Fluorouracil + cisplatin	Fluorouracil a 800 mg/m 	Days 1, 2, 3, 4 and 5	Days 1, 2, 3, 4 and 5	Days 1, 2, 3, 4 and 5	Days 1, 2, 3, 4 and 5	Days 1, 2, 3, 4 and 5	Days 1, 2, 3, 4 and 5
	Cisplatin a 80 mg/m 	Day 1	Day 1	Day 1	Day 1	Day 1	Day 1

a Fluorouracil and cisplatin will be given every 4 weeks. FP dose on Day 1 is administered within 3 days before or after the scheduled date if necessary.

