## 7.6.7 Immune Modulating Medication

Immune modulating concomitant medications are medications entered on an immune modulating medication form or available from the most current pre-defined list of immune modulating medications. The list of anatomic class, therapeutic class and generic name used for the selection at the time of the database lock will be provided.

The percentage of subjects who received immune modulating concomitant medication for

- management of adverse event
- premedication
- other use
- any use
- management of drug-related select adverse event (any grade, grade 3-5) by select AE category/subcategory (EU/ROW Submissions)
- management of IMAEs (any grade, grade 3-5) by IMAE category (US Submission) will be reported separately for each treatment group (percentages of treated subjects by medication class and generic term).

For each category/subcategory of drug-related select AEs (any grade, grade 3-5) and IMAEs (any grade, grade 3-5), the following will be reported for each treatment group:

• The total immune modulating medication treatment duration (excluding overlaps), duration of high dose of corticosteroid, initial dose of corticosteroid, and tapering duration (summary statistics)

Duration represents the total duration the subject received the concomitant medication of interest. If the subject took the medication periodically, then DURATION in the summation of all use. Initial dose represents the dose of the concomitant medication of interest received at the start of the event. In the case multiple medications started on the same date, the highest equivalent dose is chosen and converted to mg/kg by dividing by the subject's recent weight.

These analyses, except the ones related to IMAEs will be conducted using the 30-day safety window. The analyses related to IMAEs will be conducted using the 100-day safety window.

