#### 7.6.10 Immune Mediated Adverse Events

IMAEs will be summarized by treatment group for each immune-mediated category / PT using the 100-day safety window:

- Overall summary of non-endocrine IMAEs by worst CTC grade (any grade, grade 3-4, grade 5) where immune modulating medication was initiated presented by Category / PT.
- Overall summary of endocrine IMAEs by worst CTC grade (any grade, grade 3-4, grade 5) presented by Category / PT.
- Overall summary of non-endocrine IMAEs leading to discontinuation by worst CTC grade (any grade, grade 3-4, grade 5) where immune modulating medication was initiated presented by Category / PT.
- Overall summary of endocrine IMAEs leading to discontinuation by worst CTC grade (any grade, grade 3-4, grade 5) presented by Category / PT.

- Overall summary of non-endocrine IMAEs leading to dose delay or reduction by worst CTC grade (any grade, grade 3-4, grade 5) where immune modulating medication was initiated presented by Category / PT
- Overall summary of endocrine IMAEs leading to dose delay or reduction by worst CTC grade (any grade, grade 3-4, grade 5) presented by Category / PT.
- Summaries of time-to onset and time-to resolution of non-endocrine IMAEs where immune modulating medication was initiated presented by Category.
- Summaries of time-to onset and time-to resolution of endocrine IMAEs presented by Category.

A by-subject listing of IMAEs will be provided. By-subject listings of time-to resolution for longest IMAEs cluster (any grade and grade 3-5 in separate summaries) will also be provided. For new studies which collect investigator assessment of potential IMAE data, a by-subject listing of AEs considered as immune-mediated events per investigator but not qualified for IMAEs definition will also be provided.

In addition, for all Nivolumab and/or Ipilimumab treated subjects who experienced at least one IMAE, the following data presentation will be provided:

• Summary of subjects who were re-challenged with Nivolumab and/or Ipilimumab by IMAE category, with extended follow-up

For these, re-challenge is considered to have occurred when last Nivolumab and/or Ipilimumab infusion was administered after the onset of an IMAE.

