#### **Time-to resolution definition**

In order to derive the time-to resolution, overlapping or contiguous AEs within a specific category or subcategory will be collapsed into what will be termed "clustered" AEs. For example, if a subject (without pre-treatment AE) experienced an AE from 1st to 5th January, another AE (with different PT but within same category) from 6th to 11th January and same AE from 10th to 12th January, these will be collapsed into one clustered AE from 1st to 12th January. Table 10-5 is summarizing key derivation steps for each type of clustered AEs.

Time-to resolution of AE (any grade) for a specific category is defined as the longest time from onset to complete resolution or improvement to the grade at baseline among all clustered AEs experienced by the subject in this category per adverse event criteria category. Events which worsened into grade 5 events (death) or have a resolution date equal to the date of death are considered unresolved. If a clustered AE is considered as unresolved, the resolution date will be censored to the last known alive date. Improvement to the grade at baseline implies that all different events in the clustered adverse event should at least have improved to the corresponding (i.e. with same preferred term) baseline grade. This measure is defined only for subjects who experienced at least one AE in the specific category.

The time-to resolution of AE (grade 3-5) for a specific category is defined similarly with an onset date corresponding to a grade 3-5 AE.

Time-to resolution of drug-related AE (any grade or grade 3-5) for a specific category is defined similarly but restricted to drug-related AE.

The time-to resolution of AE (any grade or grade 3-5, drug-related or all) where immune modulating medication was initiated is defined similarly. For data presentation not restricted to IMAE, the additional condition that the subject started an immune modulating medication during the longest AE resolution period will be applied.

Time-to resolution for a specific subcategory is defined similarly but restricted to event of this subcategory.

Table 10-5: Derivation of clustered AE

Type of clustered AE	Derivation
Any grade	Collapse any on-treatment AE from the same category
Drug-related of any grade	Collapse any on-treatment drug-related AE from the same category

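### The select-AE time-to-resolution subset with immune-modulating medication is chosen by timing alone, so antiemetic dexamethasone can bring Arm B and C events into it

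*SAP*

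**What the plan says.** **The subset.** SAP 7.6.6.3 lists two time-to-resolution summaries. One covers all drug-related select AEs. The other covers "drug-related select AE (any grade, grade 3-5) where immune modulating medication was initiated, by treatment group". The sentence defining the second restricts it to "treated subjects who experienced the specific events and who received immune modulating medication during the longest select AE".

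**The appendix.** For presentations not restricted to IMAEs, SAP Appendix 3 adds the condition that "the subject started an immune modulating medication during the longest AE resolution period will be applied".

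**The drugs.** SAP 7.6.7 takes them from a dedicated form or, failing that, from those "available from the most current pre-defined list of immune modulating medications". It tabulates their use as management of an adverse event, premedication, other use and any use, with further rows for management of drug-related select AEs and of IMAEs. Total duration, high-dose steroid duration, initial dose and taper are then summarised by event category.

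**The background steroid.** Protocol 4.5.1.2 and 4.5.1.3 recommend dexamethasone, or an equivalent corticosteroid, as an antiemetic with fluorouracil/cisplatin, dosed by local standards. They add "Dexamethasone is allowed as premedication in arm B during the platinum-based chemotherapy" and "Dexamethasone is allowed as premedication in arm C during the platinum-based chemotherapy". Protocol 4.5.1.1 recommends no premedication for Arm A.

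**The concern.** The second summary is meant to show how long select AEs last when they needed an immune-modulating drug. For that, membership should depend on why the drug was given. As written, it depends on whether a listed drug was present, or newly begun, while the event was open. A corticosteroid given against cisplatin emesis on Day 1 of a cycle meets that test if it falls inside the event.

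The exposure differs by arm. Arms B and C have a recommended steroid premedication recurring with each 4-week cycle, and Arm A has none. A summary shown by treatment group could therefore mix treated and coincidental events in two arms, one of them the control arm without immunotherapy, and largely avoid this in the third. What is at stake is the reading of descriptive safety tables. Alpha, power and the efficacy endpoints are not involved.

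**Working it through.** The plan states no figure to reproduce. The check compares the rules and then tests how far a simple overlap calculation can be taken.

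**1. Which outputs carry a purpose criterion?**

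| SAP place | Output | Medication criterion |
|---|---|---|
| 7.6.5 | AEs with immune-modulating medication | purpose (the AE *required* it) |
| 7.6.6.1 | select-AE incidence | none |
| 7.6.6.3 | time to resolution, medication subset | timing (*initiated* in the bullet, *received* in the restriction) |
| Appendix 3 | same analysis | timing (*started*) |
| 7.6.7 | percentage using such drugs, by category | purpose (management) |
| 7.6.7 | duration, initial dose, taper by category | not stated |
| 7.6.10 | non-endocrine IMAE tables | *initiated*; no attribution rule in the SAP text |

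So the SAP distinguishes purpose elsewhere but does not carry it into 7.6.6.3 or Appendix 3. The three verbs also select different subjects: a steroid begun before onset and continued is received but not started during the event.

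**2. Does *started* remove the problem?** No. Each cycle's premedication is a new start.

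**3. Chance overlap (illustration only).** Assumptions, none of them from the documents except the 28-day cycle: dexamethasone for k days from Day 1 of every cycle, event onset uniform over the cycle, event length d days, chemotherapy continuing on schedule.

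- *Received*: d + k − 1 of the 28 onset days give overlap, so P = min(1, (d + k − 1)/28).
- *Started*: d of the 28 onset days include a Day 1, so P = min(1, d/28).

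| d (days) | *started*, any k | *received*, k = 1 | k = 3 | k = 5 |
|---|---|---|---|---|
| 7 | 7/28 = 25% | 25% | 9/28 = 32% | 11/28 = 39% |
| 14 | 14/28 = 50% | 50% | 16/28 = 57% | 18/28 = 64% |
| 28 | 100% | 100% | 100% | 100% |

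**4. Why these are not trial estimates.** The last assumption fails for many events. Protocol 4.5.2.2 delays both chemotherapy drugs on Day 1 for most Grade 2 or higher non-skin, non-hematologic drug-related events, for Grade 3 or higher skin events, and for Grade 3 or higher laboratory abnormalities with listed exceptions. Under 4.5.2.3, meeting the nivolumab delay criteria also delays chemotherapy in Arm B. Sections 4.5.4.2 and 4.5.4.3 then require recovery before restarting. While chemotherapy is held, its premedication is not due.

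**5. What overlap remains?**
- Grade 1 events, lower-grade skin events and laboratory events below the delay threshold.
- Cycles in which only one of the two agents is omitted (4.5.2.2, Rescheduling).
- The tail of a higher-grade event. Chemotherapy may generally resume at Grade 1, but Appendix 3 keeps the event open until complete resolution or return to the baseline grade. Pulmonary toxicity, diarrhea and colitis must first return to baseline under 4.5.4.2, so they contribute little here.

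**The case against.** **Purpose may already be handled.** SAP 7.6.7 separates management from premedication, and its by-category rows concern management only. The duration, dose and taper summaries follow directly and refer to the medication of interest, so they may be meant to inherit that purpose. This is a fair reading and is why they are called ambiguous rather than wrong. It does not reach 7.6.6.3 or Appendix 3, which state their own rule. The form and drug list could exclude antiemetic use, but they are not in the documents.

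**A reader might infer that immune-related events as a whole are identified by concomitant medication.** They are not. Select-AE incidence (7.6.6.1) and the endocrine IMAE tables have no such criterion, and the unrestricted time-to-resolution summary is reported as well.

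**A reader might infer that IMAE counts are inflated in Arms B and C.** The non-endocrine tables do use "where immune modulating medication was initiated presented by Category / PT", without an attribution rule. However, Appendix 3 limits its timing condition to presentations not restricted to IMAEs, Protocol 6.7.1 defines IMAEs by mechanism, and the qualifying definition that 7.6.10 relies on is not given. The effect is unknown.

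**A reader might infer that every chemotherapy cycle brings dexamethasone and that Arm A has no comparable exposure.** The protocol recommends and allows it; it does not mandate it. In Arm A, Protocol 4.5.8 allows corticosteroid premedication after a Grade 2 infusion reaction, and 3.4.3 allows brief prophylactic courses. The contrast holds for routinely recommended premedication only.

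**The direction of any bias is not established.** Longer events are more likely to overlap a dose by chance, which could lengthen the median time to resolution. Adding mild events could shorten it.

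**Conclusion.** The point stands in a limited form. Followed as written, 7.6.6.3 and Appendix 3 can place an Arm B or C event in the medication subset on the strength of an antiemetic dose, and routine premedication does not create the same route in Arm A. The by-category duration, dose and taper summaries in 7.6.7 leave the same question open.

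The consequence is confined to descriptive safety summaries and falls mainly on low-grade, skin or laboratory events. No trial-specific size can be given, because the documents contain neither event durations nor actual dexamethasone use. The percentages in the illustration are at most an upper guide for low-grade events during uninterrupted chemotherapy. The conclusion assumes that antiemetic corticosteroids are on the form or list; the premedication row in 7.6.7 makes that plausible but does not prove it.

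**What to change.** - In SAP 7.6.6.3, Appendix 3 and the by-category duration, initial-dose and taper summaries of 7.6.7, count only records whose recorded use is management of an adverse event. Exclude premedication and antiemetic use.
- Choose one of *received*, *initiated* and *started*, and use it throughout.
- State whether the IMAE outputs in 7.6.10 apply the same purpose filter, and cite the IMAE definition used.
- Keep the premedication row in 7.6.7 as a separate description.

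The cost is a few sentences of SAP text and a filter on a use category that 7.6.7 already tabulates. The downside is that records with no stated reason need a default rule. Set it before the tables are run, and report how many records it affects by arm.
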